6.3. Donor Organ Selection Criteria

Broad goal: To include donors with confirmed HCV-infection expected to have acceptable post-transplant graft outcomes based on large retrospective lung transplant studies.

Inclusion criteria for donors

- Detectable HCV RNA
- Age ≤55 years
- $\text{PaO}_2/\text{FiO}_2 \geq 300$ on $\text{FiO}_2 = 100\%$ and PEEP=5
- Cigarette use history ≤ 20 pack years
- No evidence of cirrhosis
- No prior treatment of HCV with a DAA-based therapy
- Can be isolated hepatitis B Core IgG positive, but cannot have a detectable HBV Core IgM, HBSAg, and/or HBV DNA (positive HBV NAT test)

Donor Exclusion Criteria

- Donation after circulatory death determination (DCDD)
- HIV positive

6.3.1. Donor Evaluation

We will ensure that subjects only receive a lung transplant from a confirmed HCV-infected donor as demonstrated by HCV NAT results reported by UNOS or the organ procurement organization.

6.3.2. Genotype guided treatment of HCV

We will accept donor or recipient HCV genotype results for guidance of appropriate antiviral therapy for recipients. The ability to obtain donor blood for HCV genotype testing prior to transplant will not be required.

Where available, donor genotyping will be performed on specimens provided to the Molecular Pathology Laboratory by LABS and Gift-of-Life, the local organ procurement organization. These specimens will be taken from potential lung donors once Gift-of-Life has been notified of the potential donor and will be qualified for testing by Gift-of-Life. Per standard of care, LABS will analyze specimens for the presence of HCV via serological testing and qualitative nucleic acid testing. If a specimen is positive for both HCV tests, it will be couriered to the University of Pennsylvania via a Gift-of-Life courier

In other instances, we will perform genotyping of the lung recipient in the first week after transplantation. The assay that will be used for HCV genotyping is a laboratory-developed assay that was validated by the HUP MPL under the guidance of [name] [name], PhD. The validation process entailed testing multiple past clinical samples with known HCV genotypes, as well as purchased HCV genotype controls, and assessing concordance between the results obtained and the expected results.¹⁰ This assay (the eSensor® HCVg Direct Test, GenMark Diagnostics) has also been validated by multiple external laboratories with the following results: Covance Central Laboratory Services (482 samples, 98.6% concordance), University of Minnesota (135 samples, 96.4% concordance), and the University of Washington (77 samples, 97.4%).¹¹⁻¹³ In the HUP MPL, overall, the assay was able to genotype all purchased controls correctly (n=15, HCV genotypes 1 through 6, concordance = 100%). It was also able to correctly genotype the vast majority of prior clinical samples (n=56 of 61, HCV genotypes 1 through 6, concordance = 92%). Resolution of discordant samples showed that the limitations of the assay, as determined by the validation, included decreased ability to genotype samples with: low viral loads, mixed genotype infections, or HCV genotype 4f infection. These limitations are felt to be minor as low viral load specimens are not expected from HCV-untreated organ donors, and mixed genotype / genotype 4f specimens are very rarely encountered in the United States. The validation samples were picked to better understand the limitations of the assay and so had a higher proportion of mixed infection samples (n=6) and rare genotype samples (e.g., Type 4f, n=1) than what is encountered clinically. A retrospective review by the MPL of HCV genotypes resulted at HUP over a 14-month period (July 2014 to October 2015) by the previous MPL HCV genotyping assay (Siemens VERSANT HCV Genotype 2.0) found a total of 6 mixed infections and one genotype 4f infection out of 1,551 samples tested (~0.4% and 0.06%, respectively).

6.3.3. Drug Resistance Testing

Participants with Genotype 1a and Genotype 1 HCV infection with an unknown subtype will have baseline NS5A drug resistance assay testing checked at the start of treatment. The Hepatitis C Viral RNA Genotype 1 NS5a Drug Resistance test will be used to check for NS5A drug resistance. This test uses reverse transcription polymerase chain reaction (PCR) and DNA sequencing to detect mutations [resistance associated variants (RAVs)] in the NS5a inhibitors. It has not been cleared or approved by FDA but has been validated pursuant to the CLIA regulations. The test will be performed by a lab qualified by the Principal Investigator Team. It has an analytical sensitivity of >95% for viral loads \geq 1800 IU/mL.¹⁴ Reported results include mutations and polymorphisms

associated with NS5A inhibitor resistance (only if HCV genotype 1a, 1b, or 1 detected) as well as a patient specific interpretation:

- Resistance predicted: ≥ 1 mutation predicting NS5A inhibitor resistance detected
- Resistance not predicted: no mutations predicting NS5A inhibitor resistance detected

7 CHAPTER 4: TREATMENTS

7.1. Zepatier (grazoprevir and elbasvir) for lung recipients with HCV genotype 1 or genotype 4 infection

Zepatier tablets will be provided by Merck as part of this investigator-initiated protocol funded by Merck. Open-label Zepatier (grazoprevir 100 mg and elbasvir 50 mg) will be administered once daily by mouth for 12 weeks. An exception to the 12 week course of treatment will be if patients have polymorphisms at positions M28, Q30, L31, and/or Y93 as determined by the Hepatitis C Viral RNA Genotype 1 NS5a Drug Resistance test. In this case, treatment with Zepatier will be extended to 16 weeks and renally-adjusted Ribavirin will be initiated at the clinician's discretion, and continued for the remainder of therapy (until the 16 week mark). Such a strategy will provide optimal treatment, without delaying therapy prior to receipt of results of NS5A drug resistant testing. Grazoprevir (GZR) / elbasvir (EBR) is a fixed-dose combination tablet without ribavirin.

GZR is an HCV ns3/4a inhibitor while EBR is an HCV NS5A inhibitor. Both are direct-acting antivirals, which together form an effective therapy for HCV virus and reduce the likelihood and effects of long-term liver-related HCV complications. GZR/EBR exhibits broad in vitro activity against most HCV genotypes and in vitro activity against many clinically relevant resistance-associated variants (RAVs).

Zepatier (GZR/EBR) has been evaluated globally in multiple phase I, II, and III trials to treat HCV. Randomized, placebo-controlled trials have been completed and led to obtain FDA approval for Zepatier as a treatment for genotype 1 and 4 HCV. As of July 1, 2015, a diverse population of over 1000 HCV patients has been exposed to Zepatier either as a single agent or in combination with ribavirin or sofosbuvir in phase I/II/III studies. Zepatier has been generally well tolerated at doses of 50-100 mg GZR and 50 mg EBR orally once daily. It has been comparably effective across all subgroups it has been tested in, including non-cirrhotic and/or treatment-naïve subjects.

For recipients transplanted with a lung from a donor with genotype 2, 3, 5, or 6, we plan to administer a treatment regimen of 12 weeks of Epclusa (Sofosbuvir/Velpatasvir). This treatment regimen, similar to Zepatier, has demonstrated SVR-12 (cure) rates of genotype 1 and 4 HCV that exceeds 95%. However, Epclusa has also been shown to have cure rates of 95-100% in patients with genotypes 2, 3, 5, or 6, and is thus considered a pan-genotypic HCV regimen.^{4,5} There are also multiple published case series of Epclusa being administered crushed and placed down an enteral feeding tube (e.g., NG feeding tube), including in lung transplant recipients acutely infected with HCV.^{6,7} In addition to demonstrated efficacy when crushed and administered via an enteral feeding tube (which is commonly required in lung transplant recipients), Epclusa has been shown to be safe to be administered in patients with renal dysfunction.^{8,9} Because of the interaction between Sofosbuvir and Amiodarone that can lead to fatal bradyarrhythmias, patients on amiodarone (at enrollment or pre-transplant) will be excluded. The side effect profile of Epclusa is similar to that of Zepatier from the Epclusa registry trials.

7.1.2. Administration of Zepatier

Merck & Co will manufacture, package, and label Zepatier drug. There will be one bottle per subject containing a 28-day supply (28 capsules) of 100/50 mg Zepatier tablets. Daily dose will be one tablet.

The Investigational Drug Services (IDS) pharmacy, directed by [name], will only be required to store and distribute Zepatier. Sofosbuvir and Ribavirin will be purchased and sourced locally. Both of these medications will be purchased and stored by the IDS pharmacy at Penn. Ribavirin will be generic and the manufacturer will vary depending on monthly price fluctuations.

Zepatier will be picked up from the investigational drug services (IDS) pharmacy by the research staff at 28-day intervals. The study staff will deliver the medication to the subjects at their study visits (patients expected to be at home by the time that HCV therapy is initiated and patients will be given medication at their scheduled post-transplant/study visit). Treatment with the study drug will begin within 4 weeks post-transplant. If hepatitis C is not cured after a subject has received Zepatier, he or she will be treated with a second regimen that includes Zepatier plus Sovaldi (Sofosbuvir) and Ribavirin. Any patient (male or female) receiving ribavirin as part of the first- or second-line regimen will be required to use two methods of birth control while on Ribavirin therapy, with continuing two forms of birth control for up to 6 months after the last dose of the study drug.

If patients have baseline NS5A drug resistance assay testing that demonstrates polymorphisms at positions M28, Q30, L31, and/or Y93, treatment with Zepatier will be extended to 16 weeks, rather than 12 weeks, and renally-adjusted Ribavirin at the clinician's discretion will be initiated, and continued for the remainder of therapy (until the 16 week mark). Such a strategy will provide optimal treatment, without delaying therapy prior to receipt of results of NS5A drug resistant testing.

7.1.3. Drug logistics and accountability

Study medication bottles must be stored at controlled temperature of 20°C to 25°C (68°F to 77°F); excursions permitted between 15°C to 30°C (between 59°F to 86°F) in a locked, secure area. Study drug must be protected from moisture. The research staff or investigator will instruct the subject on the proper administration of Zepatier. Zepatier tablets should be taken once daily by mouth. The investigator, or a responsible party designated by the investigator, must maintain a careful record of the inventory and disposition of the investigational agent using the drug accountability form. If a subject loses the bottle of study medication, the

research staff should contact [name], Pharmacist at the research pharmacy. A replacement bottle with the appropriate amount of study medication will be made available at the research pharmacy.

7.1.4. Destruction and return

At the conclusion of the study, remaining medication from the study patients (and left-over medication) will be destroyed at the clinical site, after approval is granted by the research pharmacy for the drug destruction plan. Destruction will be documented in the drug accountability form.

7.1.5. Zepatier Initial Treatment Failures

Study subjects with treatment failure, defined as virologic breakthrough (when an undetectable viral load while on treatment becomes detectable) or virologic relapse (undetectable viral load after completion of Zepatier treatment that during the 12-week post-treatment follow-up period becomes detectable) will be provided open-label Zepatier + Sofosbuvir (Sovaldi) 400 mg + Ribavirin (generic), renally dosed based on creatinine clearance per the manufacturer guidelines. Any subjects who experience treatment failure will repeat the original study lab visit and visit protocol once they begin their secondary treatment with Zepatier, sofosbuvir, and ribavirin, similar to subjects initiating HCV treatment following lung transplantation. Prior to initiating treatment with this regimen, patients will have serum NS5A resistance (RAV) testing.

7.2. Epclusa for lung recipients with genotype 2, 3, 5, or 6 HCV infections

Upon receiving the results of genotype testing of the donor and/or lung recipient showing HCV infection that is neither genotype 1 nor genotype 4 (genotypes 2, 3, 5 or 6), PIs will begin Epclusa that will be locally sourced by the hospital pharmacy. In the unlikely event that the patient has a contraindication to Epclusa, another optimal antiviral regimen will be selected.

The Hospital of the University of Pennsylvania (HUP) will provide the antiviral treatment and coordinate the application to the subjects insurance company for coverage of the antiviral treatment. In the event that the subject's insurance company denies coverage for the antiviral treatment, HUP will provide the entire HCV treatment regimen at no charge to the subject. In the event that the subject fails to be cured of HCV with the initial treatment regimen and the subject's insurance declines to pay for a second antiviral treatment, HUP will provide the second HCV treatment regimen at no charge to the subject.

8 CHAPTER 5: DATA COLLECTION

8.1. Study visits

Study visits are scheduled to occur following subjects' standard post-transplant follow-up visits. Since treating cardiologists do not always require stable post-transplant patients to attend these visits, subjects may be asked to come in solely for study visits. These visits will be encouraged, but not required unless the study drug is being dispensed that day. For all other study visits, a missed visit by a stable subject who has had necessary labs drawn will not be considered a protocol violation.

8.1.1. Informed consent

During the screening phase, potentially eligible, interested subjects will be invited to attend an informational session. The following procedures will be performed during the screening process:

- Sign and date the ICF and HIPAA authorization
- Review of inclusion/exclusion criteria
- Schedule for screening visit

After completing the informational session and signing the informed consent, the subject will be scheduled for a screening visit within 56 days if the subject meets inclusion/exclusion criteria thus far. The study staff will call the subject 1-2 days prior to the screening visit and send a reminder letter as well if the screening visit is not conducted within the 2 weeks following consent. The study staff will instruct the subject to not eat or drink (except water) and to avoid heavy exercise for 3 hours prior to the study visit in order to ensure accuracy of the Fibroscan test that requires 3 hours of NPO prior to testing. According to the recommendations of use and based on safety and efficacy matters; patients with ascites (fluid in the abdomen), persons with active implantable medical devices, and persons with a waist size more than 100cm will be excluded from having a Fibroscan performed.

8.1.2. Screening

The following procedures and activities will be performed during the screening process, after the informed consent is signed:

- Review medical history
- Vital signs
- Physical exam
- Fibroscan
- Review current medications
- Labs/phlebotomy: hepatic function panel, HCV RNA, HBV DNA, and HIV antibody
 - HBV Core Antibody will be checked in patients during screening, if not checked previously.
- Serum chg. pregnancy test (for women of childbearing potential)
- Completion of health status questionnaire (RAND-36)
- Provide instructions on recording of new medications and dose changes

8.1.3. Post-Lung Transplant

8.1.3.1. Post-Lung Transplant Visits

Patients, after receiving a lung transplant are followed very closely by both the surgical and nephrology team. As a part of standard of care visits, the following procedures activities will be performed:

- Phlebotomy
- Vital signs
- Physical exam

The study staff will follow procedures and activities closely along with transplant team and this information (vital signs, physical exam, and phlebotomy results) will be collected as a part of data collection. In addition to these standard of care procedures and activities, the study team will also perform specific research related activities at specific time points.

8.1.3.2. Post-Lung Transplant Research Phlebotomy

Research laboratory blood draws will take place along with standard of care blood draws outlined in Section 8.2.1. The study staff will call the research subject to coordinate research blood draws appropriately. In addition, study staff will assess for adverse events/side effects and obtain current medication data.

As outlined in Section 8.2.1, patients with a positive HBV Core Antibody, HBV-DNA levels will be checked every 6 weeks while on Zepatier and LFTs will be closely monitored. HBV therapy may be considered the transplant team as medically appropriate.

Additional laboratory testing will be done if the PIs feel it is necessary for patient safety.

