8.1.3.3.2. Management of patients with positive HBV Core Antibody

For patients with a positive HBV Core Antibody, HBV-DNA levels will be checked every 6 weeks while on Zepatier (or Epclusa or another appropriate antiviral treatment) and LFTs will be closely monitored. HBV therapy may be considered the transplant team as medically appropriate.

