8.2. Study schedule of procedures

8.2.1. Visits, lab testing, and other clinical testing

See next page for table.

Transplanting HCV Lungs into HCV Negative Lung Recipients

Protocol V5.0, November 2020

Week(s) post-KT		Day(s) post-KT		Visit Schedule		Research Visit Activities					Research Labs					Standard of Care								
Week(s) post-KT	Day(s) post-KT	Visit	Study Visits	Lab-Only	Informed Consent	Assess Adverse Events	Current Medications	Fibroscan	RAND-36 Questionnaire	HBV DNA HIV AB & LFTs	HBV Core Antibody	Urine Preg Test	Urine Protein/Cre Ratio	HCV RNA	Viral Kinetics (optional)♦	NSSA Resistance**	Genotyping of donor and/or recipient	Vitals & Physical Exam	Surveillance biopsy	CMP*	CBC	Tacrolimus		
Screening					✓	✓	✓	✓	✓	✓	✓	✓	✓	✓				✓						
1 (Begin treatment)	Day 2 - 7	V1	✓			✓	✓				✓■			✓	✓	✓	✓	✓	✓	✓	✓	✓		
1	7 ± 1 day			✓			✓							✓	✓					✓	✓	✓	✓	
2	10 ± 1 day	V2	✓			✓	✓							✓	✓				✓	✓	✓	✓	✓	
2	14 ± 1 day			✓			✓							✓	✓				¥	✓	✓	✓	✓	
3	21 ± 3 day	V3	✓			✓	✓							✓	✓				✓	✓	✓	✓	✓	
4	28 ± 3 day	V4	✓			✓	✓	✓	✓					✓	✓	✓			✓	✓	✓	✓	✓	
6	42 ± 7 day	V5	✓			✓	✓				✓■			✓	✓				✓	✓	✓	✓	✓	
8	56 ± 7 day	V6	✓			✓	✓							✓	✓				✓	✓	✓	✓	✓	
10	70 ± 7 day	V7	✓			✓	✓								✓				✓	✓	✓	✓	✓	
12	84 ± 7 day	V8	✓			✓	✓				✓■			✓	✓	✓			✓	✓	✓	✓	✓	
13 (End treatment)†	91 ± 7 day			✓			✓								✓									
16 (SVR 4)†	112 ± 14 day	V9	✓†			✓	✓							✓	✓			✓†	✓	✓	✓	✓	✓	
20 (SVR 8)	140 ± 7 day			✓										✓	✓				✓	✓	✓	✓	✓	
24 (SVR 12)	168 ± 14 day	V10	✓			✓		✓	✓					✓	✓	✓			✓	✓	✓	✓	✓	
28†	196 ± 7 day			✓											✓					✓	✓	✓	✓	✓
32	224 ± 7 day			✓											✓					✓	✓	✓	✓	✓
36 (SVR 24)	252 ± 7 day			✓										✓	✓	✓			✓	✓	✓	✓	✓	
40	280 ± 14 day			✓										✓					✓	✓	✓	✓	✓	
52	365 ± 14 day	V11	✓			✓		✓	✓					✓	✓	✓			✓	✓	✓	✓	✓	

* CMP=comprehensive metabolic panel which includes basic metabolic panel and liver function tests
care blood draw

** As appropriate ♦Viral Kinetics testing can be done anytime there is a standard of

[†]If patients require the 16 weeks of therapy, the last 4 weeks would be the same as weeks 9-12 of therapy [■]Only if HBV Core Antibodies are positive.

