8.2.2. Blood sampling volumes

Maximum Post-Transplant Blood Draw Totals								
Week Post-KT	CBC	CMP	Tacrolimus/ Cyclosporine	HBV Core Antibody	HCV RNA	Viral Kinetics (optional)♦	NS5A Resistance	Blood Draw Total
1	4	4.5	4	4	6	6	2	28.5
1	4	4.5	4	0	6	6	0	24.5
2	4	4.5	4	0	6	6	0	24.5
2	4	4.5	4	0	6	6	0	24.5
3	4	4.5	4	0	6	6	0	24.5
4	4	4.5	4	0	6	6	0	18.5
6	4	4.5	4	4	6	6	0	24.5
8	4	4.5	4	0	6	6	0	24.5
10	4	4.5	4	0	0	6	0	18.5
12	4	4.5	4	4	6	6	0	28.5
16	4	4.5	4	0	6	6	0	24.5
20	4	4.5	4	0	6	6	0	24.5
24	4	4.5	4	0	6	6	0	24.5
28	4	4.5	4	0	0	6	0	18.5
36	4	4.5	4	0	6	6	0	24.5
40	4	4.5	4	0	0	6	0	18.5
52	4	4.5	4	0	6	6	0	24.5
Total	68	76.5	68	0	84	102	2	400.5

♦ Lung transplant recipients have twice a week labs including tacrolimus or cyclosporine levels, CBC and a CMP after discharge for the first 6-8 weeks

♦ There may also be additional blood draws due to optional Viral Kinetics lab testing increasing the total sample volume.

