12.4.2. Serum virologic testing

- HCV RNA (with Genotyping per protocol)
- Hepatitis B surface antigen
- HIV antibody testing.
- HBV Core Antibody (as needed)

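### Sections 8.2.1 and 8.2.2 label the conditional on-treatment hepatitis B draws as core antibody, although the text requires HBV DNA and cites 8.2.1 for it

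*Combined protocol and SAP*

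**What the plan says.** Two passages of text set the monitoring rule. Section 8.1.3.2: "As outlined in Section 8.2.1, patients with a positive HBV Core Antibody, HBV-DNA levels will be checked every 6 weeks while on Zepatier". Section 8.1.3.3.2 extends it beyond Zepatier: "HBV-DNA levels will be checked every 6 weeks while on Zepatier (or Epclusa or another appropriate antiviral treatment". Both add close monitoring of liver tests and leave HBV therapy to the transplant team.

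Core antibody is a screening test in the text. Section 8.1.2 says "HBV Core Antibody will be checked in patients during screening, if not checked previously", and it lists the screening bloods as "hepatic function panel, HCV RNA, HBV DNA, and HIV antibody".

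The schedule in 8.2.1 has two hepatitis B columns. One is headed "HBV DNA HIV AB & LFTs" and the other HBV Core Antibody. A footnote marks certain ticks "Only if HBV Core Antibodies are positive". The blood-volume table in 8.2.2 has one hepatitis B column, "HBV Core Antibody". Section 12.4.2 lists "HBV Core Antibody (as needed" as needed and does not list HBV DNA.

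**The concern.** Section 8.1.3.2 relies on 8.2.1 to carry the HBV DNA rule, and the visit instructions send staff to 8.2.1 for the full list of research bloods. If the schedule names a different test, staff who order from it will order the wrong one.

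The two tests answer different questions. Core antibody shows past exposure, which is already known in these subjects. HBV DNA shows whether the virus is replicating, and that is what a decision on HBV therapy during antiviral treatment needs.

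Affected subjects can be enrolled. Section 6.2.2 excludes patients who are positive for surface antigen or HBV DNA, but not those who are positive for core antibody only.

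**Working it through.** No sample size, power or error rate is involved. The check sets text against tables and asks whether PDF extraction could have produced the mismatch.

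**Table 8.2.1.** It has 23 column headers and 20 rows (screening plus 19 post-transplant). Column 11 is the HBV DNA bundle and column 12 is HBV Core Antibody.

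| Row | Column 11 (HBV DNA bundle) | Column 12 (HBV Core Antibody) | Alignment |
|---|---|---|---|
| Screening | ticked | ticked | fits the headers; agrees with 8.1.2 |
| Week 1, V1 | blank | conditional tick | exactly 23 cells |
| Week 6, V5 | blank | conditional tick | 24 cells, surplus cell to the right of column 16 |
| Week 12, V8 | blank as extracted | conditional tick as extracted | 24 cells, ambiguous |

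- *Week 6.* The next ticks fall in columns 15 and 16 (HCV RNA and viral kinetics). Table 8.2.2 shows 6 and 6 for those tests at week 6. Shifting these cells one column left would lose viral kinetics, so the row is aligned through column 16.
- *Week 12.* The extracted row has a tick under NS5A resistance, but 8.2.2 gives 0 for that test at week 12. A one-cell shift is therefore possible and would move the conditional tick into column 11. I do not rely on this row and take the week 12 label from 8.2.2.
- *Other rows.* The remaining 19 − 3 = 16 post-transplant rows have no tick in columns 11 to 14, so a one-cell shift cannot create an HBV DNA tick there.

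**Table 8.2.2.** The HBV Core Antibody column shows 4 at the first week 1 row, 4 at week 6, 4 at week 12, and 0 elsewhere. There is no HBV DNA column.

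**Extraction.** The two tables are built separately and agree on the weeks, and on the label at weeks 1 and 6. A displaced cell in 8.2.1 could not rename a column in 8.2.2.

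**Text against tables.** The text asks for HBV DNA, in core-antibody-positive subjects, every 6 weeks on therapy. The tables give the same subjects and a compatible rhythm (weeks 1, 6 and 12), but name core antibody. Only the test name differs. The footnote limits the draws to subjects whose antibodies are positive, and 8.1.2 has that status established by screening. As labelled, the draw would repeat a known result and give no viral load. A mislabel is the natural reading.

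**The case against.** The mismatch itself is hard to dispute. The case against making much of it runs as follows.

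- **The intended meaning can be recovered.** The right population and the right weeks are in 8.2.1, and the right test is named twice in the text. One of those places sits within the Visit 1 instructions. No section says the table overrides the text. This stands, and it is why the point is a wrong test name and not an absent plan.
- **Other safeguards exist.** Liver tests are followed closely, 8.1.3.2 allows extra safety testing, and 12.4 allows tests as clinically indicated. These lower the chance of a missed reactivation, but they do not replace the scheduled viral load.
- **The antibody draw might be meant.** Section 6.3 accepts donors with isolated core IgG, and the footnote does not say whose antibody is positive. That leaves some doubt about intent. Even so, 8.2.1 would still lack the HBV DNA draw that 8.1.3.2 says it outlines.
- **The subgroup may be empty, and no endpoint changes.** Both are true. They limit the size of the problem but do not make the schedule correct.
- **Section 12.4.2 is weak evidence.** Agreed: it also leaves out the screening HBV DNA, so it is incomplete in general. It is cited only as a place to correct.

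**Conclusion.** The concern holds. Text and schedule name different tests for the same conditional safety draws, and the cross-reference in 8.1.3.2 is wrong as written. Three entries in each table are affected (weeks 1, 6 and 12), and neither table names HBV DNA for the conditional on-treatment draws.

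This rests on the alignment of the week 1 and week 6 rows in 8.2.1 and on the separate column in 8.2.2. For week 12 it rests on 8.2.2 alone.

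The documents do not give the number of core-antibody-positive recipients. I assume only the full possible range, 0 to 11 of the 11 treated. SVR-12 and the planned analyses are unaffected. The correction should be made because it concerns patient safety and costs almost nothing.

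**What to change.** - In 8.2.1 and 8.2.2, relabel the three conditional post-transplant entries (weeks 1, 6 and 12) as HBV DNA. Apply them to any antiviral regimen, as 8.1.3.3.2 does, and bring the Zepatier-only wording in 8.1.3.2 into line.
- In 8.2.1, give this test its own column, because the existing HBV DNA column also orders HIV antibody and liver tests.
- Keep HBV Core Antibody as a screening test.
- Add HBV DNA to 12.4.2.
- While 8.2.2 is open, correct its totals. The hepatitis B column total is printed as 0 but its entries sum to 4 + 4 + 4 = 12. The printed grand total of 400.5 omits that 12; the components sum to 412.5.

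The cost is three relabelled entries in each of two tables, one list addition and one wording change. No visits or draws are added, because the conditional slots already exist.
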